## 2.6 Rationale for Consolidative Targeted Radiation Therapy

As it is an accepted standard of care, particularly in the pediatric population, a modification of Residual PET Radiation Therapy (Residual PET RT) will be used to consolidate systemic treatment for eligible patients in either arm who do not achieve a metabolic complete response. In adults with cHL, RT does not significantly improve outcome among patients with advanced stage HL who achieve a complete response to adequate systemic therapy. For example, an EORTC randomized trial found that adjuvant RT did not improve outcome among patients with advanced stage HL who had achieved a complete anatomic response to 6-8 cycles of MOPP-ABV (84). Approximately 35% of the patients in that trial were assigned RT, however, primarily due to failure to achieve a CR. In the PET-era, the

GITIL/FIL HD 0607 trial found that consolidative RT to sites of initial bulk  $\geq 5\text{cm}$  did not significantly improve outcome for patients who had a negative PET scan after 2 cycles and were in metabolic CR after six cycles of ABVD (3-year PFS rate of 97% for RT vs 93% for no further therapy,  $P = .29$ ). (85)

However, among patients not achieving a CR, RT can effectively consolidate primary treatment and significantly reduce the risk of relapse, potentially avoiding the need for salvage chemotherapy and autologous stem cell transplant. The GHSG HD12 found that following 8 cycles of BEACOPP-based chemotherapy, patients with advanced stage HL and a residual mass  $> 1.5\text{ cm}$  who were randomized to consolidative RT had significantly better freedom from treatment failure compared to those treated with chemotherapy alone (86). This finding is consistent with results from the UKLG LY09 study demonstrating a significant improvement in both progression-free and overall survival associated with consolidative RT (not randomly assigned) in advanced stage HL patients. (87)

**The optimal time to assess PET response in order to guide RT use is uncertain. Although interim PET has been used to guide consolidative RT use in some trials, the anticipated difference in early PET response between BV-AVD and N-AVD could cause a substantial imbalance in RT exposure between treatment arms. Hence, interim PET will not be used to determine RT use in this trial.**

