**Consequently, response at the end of six cycles of systemic therapy will be used to guide the use of RT in this trial. Specifically, localized Residual PET Radiation Therapy (Residual PET RT) will be used for patients with limited residual PET-avid sites who have achieved a partial response (as per the 2014 Lugano Classification) at the completion of 6 cycles of systemic therapy on either arm.** This indication for RT to reduce the rate of relapse in this high-risk population is consistent with available evidence and with recent German Hodgkin Study Group trials. (88) This approach is anticipated to reduce the rate of RT in childhood HL patients from 60% to 15% in advanced stage HL.

In advanced-stage or high-risk patients, involved field radiotherapy (IFRT) has traditionally encompassed a large volume of normal tissue due to anatomically widespread sites of multiple disease and extra-lymphatic spread.

One of the aims of this study is to reduce the volume of radiotherapy in order to reduce potential acute and late toxicities, while maintaining disease control.

This will be done in two ways:

- 1) omitting radiotherapy (RT) among patients who have a complete response to systemic therapy (defined as Deauville 1-3 after six cycles of systemic therapy), and
- 2) limiting the volume of RT among patients who receive this treatment by employing Residual PET Radiation Therapy (Residual PET RT).

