##### a. Eligibility for protocol-specified radiation therapy Residual PET RT

1. The treating investigator must have declared intent for use of Residual PET RT at the date of registration to the protocol (and patient must meet criteria for RT indications in [Section 7.5b](#)).
2. Timing of protocol therapy administration, response assessment studies, and surgical interventions are based on schedules derived from the experimental design or on established standards of care.

Minor unavoidable departures (up to 72 hours) from protocol directed therapy and/or disease evaluations (and up to 1 week for surgery) for valid clinical, patient and family logistical, or facility, procedure and/or anesthesia scheduling issues are acceptable (except where explicitly prohibited within the protocol).

See also [Section 7.1b](#) for extended allowable windows in event of COVID-19 extenuating circumstance.

3. All investigators registering pediatric patients are required to agree to intent to apply RT per the disease and response characteristics defined below. Investigators at all other (non-COG) participating institutions will be required to have declared their intent to apply RT prior to patient registration and randomization (per [Section 5.3e](#)).
4. IROC Rhode Island will verify patient eligibility for protocol-specified RT. To allow for IROC Rhode Island review prior to RT, images must be submitted to IROC Ohio (via TRIAD preferred) as indicated in [Sections 12.3](#) and [15.4](#).

b. Indications for Radiotherapy

1. The indication for RT will be based on the end-of-treatment imaging evaluation performed upon completion of 6 cycles of systemic therapy (4-8 weeks after the last dose of study drug). In general terms, RT will be delivered when patients have 1-2 sites initially involved with HL that achieve only a partial response. Specifically, RT will be indicated when the patient has persistent sites upon completion of 6 cycles of systemic therapy that meet all of the following criteria:
  - a. Residual nodal mass  $\geq 2.5\text{cm}$  in axial diameter, or residual extranodal lesion  $>1\text{cm}$  in axial diameter (e.g. lung nodule or splenic nodule), and
  - b. Deauville score = 4 or 5 (See [Section 10.1a](#)), and
  - c.  $\geq 30\%$  reduction in maximal transverse diameter compared to pre-treatment imaging.
2. RT may be given to one or two nodal sites. RT to more than two nodal sites is not allowed.

c. Contraindications for RT:

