In the current proposal, we will assess the prognostic impact of specific genetic alterations (i.e. 9p24.1) and MTB in patients with advanced stage cHL treated on S1826. To accomplish this, we will deploy our comprehensive targeted sequencing ctDNA assay to capture the cHL molecular signature, including genetic alterations associated with sensitivity to PD-1 blockade (9,10,11,12,13). CtDNA assessment provides real-time information about tumor burden and dynamic response to therapy, non-invasive genomic profiling, and monitoring of clonal dynamics – opening the door to numerous applications that could significantly impact the care of patients with cHL. We anticipate that the use of ctDNA as a non-real time integrated biomarker in S1826 will establish the clinical utility of ctDNA in cHL as: (1) “Liquid biopsy” – given the paucity of genetic data in primary cHL, our non-invasive genomic profiling via ctDNA of adult and pediatric patients with newly diagnosed advanced stage disease will be a major contribution to the field, enabling precision medicine approaches in cHL (e.g. prioritization of anti-PD1 therapy for patients with high burden 9p24.1 alteration); (2) Prognostic biomarker – current clinical prognostic indices (e.g. IPS score) inadequately risk-stratify advanced stage cHL patients for risk-adapted therapeutic approaches; however, MTB determined by ctDNA can provide a highly sensitive measurement of tumor burden prior to therapy as a tool for refining pre-treatment risk stratification and designing clinical trials studying intensification or de-escalation of therapy; (3) Dynamic measure of response – rather than relying on imperfect PET scans, ctDNA provides real-time, highly sensitive information about molecular depth of response (i.e. MTB) that will inform ctDNA-response driven clinical trials; (4) Disease monitoring – Imaging surveillance and the detection of clinically occult relapse is not associated with improved outcomes in cHL, (14) but detection of molecular relapse using ctDNA may provide the opportunity to study pre-emptive intervention with well-tolerated novel agents to prevent clinical relapse.

As a randomized evaluation of the incorporation of PD-1 blockade into frontline therapy, our proposed S1826 ctDNA analysis can identify the patients most likely to benefit from a particular frontline immuno-chemotherapy intervention (i.e. N-

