AVD or BV-AVD) regardless of the result of the primary analysis and can inform the design of the next cHL clinical trial in the cooperative groups (e.g. response adapted therapy using ctDNA and/or PET).

We hypothesize that ctDNA will identify characteristic alterations of chromosome 9p24.1 (i.e. amplification) and genes (i.e. JAK/STAT pathway genes - SOCS1, STAT6) that result in overexpression of PD-1 ligands in cHL and that these genetic features will be selectively associated with favorable response and PFS in patients treated with N-AVD,(24, 29) but not after BV-AVD. Therefore, we are testing if treatment effect of N-AVD versus BV-AVD on PFS depends on 9p24.1 and specific gene alterations. Additionally, we hypothesize that MTB will be prognostic for PFS in patients treated with either N-AVD or BV-AVD (i.e. irrespective of regimen): (1) baseline MTB will be prognostic for PFS, (2) interim on-treatment kinetic changes in MTB (i.e. achievement of 2-log drop in MTB after 2 cycles) will be prognostic for PFS, and (3) MTB at EOT will have superior PPV and NPV to 5-point PET-CT at interim and EOT.

c. Experimental Approach and Assays

1. Sample Collection

Patients have 20mL of whole blood collected at baseline, on C3D1, at EOT, and at the time of relapse or progression (if applicable) in BCT cell-free DNA Streck tubes. Samples are shipped to the SWOG central biorepository where the whole blood is separated into plasma and buffy coat, yielding 10-12mL of plasma per time point, separated into 1mL aliquots. Samples are stored at -80C. Frozen samples will be shipped on dry ice from the SWOG biorepository to DFCI/Broad.

2. Collection Kits / Order of Sample Collection / Sample Collection and Submission Instructions

3. Description of Assay or Methods

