We will initially investigate change in MTB in a univariable setting but will also use multivariable models incorporating other demographic and clinical features from diagnosis to understand how these additional features may modify the interpretation of changes in MTB. To more clearly consider the relationship between changes in MTB and PFS outcomes, we will also perform a landmark analysis of PFS including only those patients who remain alive without progression at EOT. All assessments of MTB and PFS will rely on log rank tests in the setting of a single threshold for all patients or stratified log rank tests in the setting of customized thresholds for the age and IPS risk score strata defined in the protocol, and Cox proportional hazards models for the multivariable setting, using either stepwise selection or a lasso approach. Again, to assess overall multivariable performance, variables and cut points will be specified prior to using the Lasso. In addition, it is recognized that cross-validated partial likelihood is unstable; therefore, model selection (complexity) will use generalized cross-validation.

We will specifically assess the PPV/NPV of detectable ctDNA at EOT and compare this to the gold standard EOT PET-CT scan response according to the 2014 Lugano Classification. We assume that approximately 20% of patients will be ctDNA positive at EOT, and 10% will be PET-CT positive (Deauville Score 4-5) at EOT. With approximately 200 patient samples per arm, then the PPV for either of those measures can be estimated to within +/- 11% (95% confidence interval) for the case with 20% ctDNA positive. Analogous results hold for PET-CT and NPV.

e. Materials Handling

Frozen samples will be shipped on dry ice from the SWOG biorepository at Nationwide Children's Hospital to DFCI/Broad for analysis.

f. Funding

BIQSFP funding has been secured from NCI CTEP for the Translational Medicine analysis. Additional funding support will be provided by BMS and/or the TM investigators internal institutional funding.

g. References

- 1 Song Y, et al. A single-arm, multicenter, phase 2 study of camrelizumab in relapsed or refractory classical Hodgkin lymphoma. *Clin Cancer Res.* 2019 Aug 2016. doi: 2010.1158/1078-0432. CCR-2019-1680. [Epub ahead of print], 2019.

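### The end-of-treatment ctDNA-versus-PET comparison of PPV and NPV is confounded in two opposing directions, by PET-guided treatment and by PET defining progression, and the plan handles neither.

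*Combined protocol and SAP*

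**What the plan says.** Section 18.13b puts forward the hypothesis that "MTB at EOT will have superior PPV and NPV to 5-point PET-CT at interim and EOT". Section 18.13d, Objective 2, then plans the EOT comparison: "We will specifically assess the PPV/NPV of detectable ctDNA at EOT and compare this to the gold standard EOT PET-CT scan response". It assumes that "approximately 20% of patients will be ctDNA positive at EOT, and 10% will be PET-CT positive (Deauville Score 4-5) at EOT", with about 200 samples per arm, and says that "the PPV for either of those measures can be estimated to within +/- 11% (95% confidence interval) for the case with 20% ctDNA positive", with similar results for PET and for NPV. It names no outcome and no time horizon for PPV or NPV. PFS is the sub-study's primary clinical endpoint; EFS is one of the secondary ones.

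Elsewhere in the protocol:
- Section 7.5b, on residual PET radiotherapy: "The indication for RT will be based on the end-of-treatment imaging evaluation performed upon completion of 6 cycles of systemic therapy". A Deauville score of 4 or 5 is one of the required criteria.
- Section 2.6, on patients not in complete response: "RT can effectively consolidate primary treatment and significantly reduce the risk of relapse".
- Section 18.13b describes ctDNA as not used in real time: "We anticipate that the use of ctDNA as a non-real time integrated biomarker in S1826".
- Section 10.4 counts only Lugano progression or death as PFS events. Section 10.5 adds non-protocol systemic therapy and non-protocol radiotherapy for EFS. Protocol radiotherapy is an event under neither.
- Sections 10.1b.4 and 18.7 build PET findings into the definition of progression.

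**The concern.** PPV and NPV compare two tests fairly only if the outcome is counted independently of both. Here one of the two tests can change the outcome, and can also constitute it.

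**Treatment.** A PET-positive patient who is irradiated, or given salvage before formal progression, may never have the event that PPV counts. PET is then scored as a false positive. No one is treated because of ctDNA. Irradiating PET-positive, ctDNA-negative patients would also raise the NPV of ctDNA and leave the NPV of PET unchanged.

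**Definition.** A patient whose EOT scan meets the progression criteria counts as a correct PET prediction at the moment of the test.

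Two existing provisions look relevant but do not reach this comparison. The landmark among patients alive without progression at EOT (Section 18.13d, Objective 2) is tied to the analysis of change in molecular tumour burden and PFS. The sensitivity analysis in Section 11.1 concerns non-protocol therapy in the primary analysis. At stake is a claim about whether ctDNA outperforms PET, which the protocol says could inform the design of the next trial.

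**Working it through.** **1. The plan's precision figure.** The worst-case 95% half-width is 1.96 x sqrt(0.25/n).
- ctDNA-positive, both arms: n = 0.20 x 400 = 80, giving 11.0 points. This reproduces the stated figure, but only with the arms pooled; per arm, n = 40 gives 15.5.
- PET-positive, both arms: n = 0.10 x 400 = 40, giving 15.5 points.

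**2. How many PET-positive patients might be irradiated.** Section 11.2 expects radiotherapy almost only in paediatric patients. The tables in Section 2.9 plan 317 + 27 = 344 paediatric patients of 987, so 400 x 344/987 = 139 in the ctDNA set.
- Section 2.6 says: "This approach is anticipated to reduce the rate of RT in childhood HL patients from 60% to 15% in advanced stage HL". Then 0.15 x 139.4 = 20.9 are irradiated, about 21 of 40.
- If the 10% PET positivity applies equally at all ages, only 0.10 x 139.4 = 14 paediatric patients are PET-positive, so about 14 of 40 at most.
- The figure of 21 needs at least 20.9/139.4 = 15% positivity in paediatric patients and 19.1/260.6 = 7% in adults. The plan states neither.

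**3. Treatment effect alone.** Let p be the event risk in test-positive patients without radiotherapy, the same for both tests; r the risk after radiotherapy; m the number irradiated; and c the number of those who are ctDNA-positive.
- Observed PET PPV = p - m(p - r)/40
- Observed ctDNA PPV = p - c(p - r)/80
- Spurious gap = (p - r)(m/40 - c/80)

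Assumptions: p = 50-70%, which is not in the documents; r = 15-35%, taken from the 65-85% control quoted in Section 2.7. So p - r runs from 0.15 to 0.55.

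| Irradiated (of 40) | All ctDNA-positive | Half ctDNA-positive |
|---|---|---|
| 14 | 0.175(p - r): 2.6 to 9.6 points | 0.2625(p - r): 3.9 to 14.4 points |
| 20.9 | 0.261(p - r): 3.9 to 14.4 points | 0.392(p - r): 5.9 to 21.6 points |

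Smaller cases:
- With 6 of 40 treated (15%) and p = 50%, the gap is about 1-5 points, with 8 to 40 of the 40 PET-positive patients also ctDNA-positive.
- With p = 40%, r = 25-35% and 14 irradiated, it is about 1-4 points across the two columns.

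ctDNA NPV rises by (m - c)(p - r)/320. With half of 20.9 ctDNA-negative, that is 10.45 x (0.15 to 0.55)/320, or 0.5 to 1.8 points.

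**4. The opposing effect.** Suppose k PET-positive patients meet progression on the EOT scan, so their event is certain instead of having risk p. If the irradiated patients and these k are all ctDNA-positive, the gap closes when k = m(p - r)/(1 - p). At p = 50%:
- m = 14: k = 4.2 (r = 35%) or 9.8 (r = 15%)
- m = 20.9: k = 6.3 or 14.6

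The documents give no figure for k, so the sign of the net effect cannot be derived.

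**The case against.** A reader might infer that the comparison is simply biased towards ctDNA. The documents do not support that. PET is part of the progression definition, and step 4 shows that a handful of same-scan progressions could cancel the treatment effect. PET-positive patients may also have repeat imaging and biopsy (Section 7.4c), which can bring events to light.

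Nor does a positive PET automatically bring treatment. Radiotherapy is at the physician's discretion. It needs declared intent, no more than two sites, and size and shrinkage criteria (Section 7.5). Indeterminate scans are to be observed and re-imaged (Section 7.4c). The only salvage figure is 2 of 12 patients not in complete response after N-AVD, and salvage does not censor PFS, so later progression still counts. Section 7.4c also warns that false-positive EOT scans may be common on N-AVD, which would lower p and shrink the gap. All of this stands, and it limits the size of the treatment effect.

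Using EFS would capture salvage but not protocol radiotherapy, and would count a PET-prompted switch as an event, in PET's favour. The choice of endpoint therefore moves the result, which is a reason to fix it in advance.

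Finally, this is a secondary estimate. The primary tumour-burden analysis is the 2-log change at Cycle 3 Day 1, the PPV/NPV comparison has a precision statement but no power, and samples from the second half of accrual are held for validation. That limits the consequence. It does not make the comparison interpretable.

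**Conclusion.** The point holds as confounding in two opposing directions, with no established net sign. Carried out as written, the comparison would credit PET with progressions seen on the scan being evaluated and would also score PET against outcomes that its own result can alter.

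The treatment component alone is about 3-10 points in favour of ctDNA with 14 of 40 PET-positive patients irradiated, and about 4-14 points with 21. Both assume 50-70% risk without radiotherapy, 15-35% after it, equal true PPV and all irradiated patients ctDNA-positive. Less overlap enlarges it; lower radiotherapy use or lower untreated risk shrinks it. It can therefore be of the same order as the stated +/-11 points. That PFS is the intended outcome is an inference from its place as the sub-study's primary clinical endpoint.

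The mechanism and the omission are clear from the text; the size is illustrative. It would go too far to say that half of PET-positive patients will be irradiated, or that the main result of Objective 2 is an artefact. The randomised PFS comparison is not affected.

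**What to change.** In Section 18.13d, Objective 2:
1. Name PFS from EOT at a fixed horizon (for example 2 years) as the outcome for PPV and NPV. Restrict the comparison to patients alive and progression-free at the EOT scan, extending the landmark already planned there. This removes same-scan events but not the treatment effect, so the next two items are also needed.
2. Report Kaplan-Meier PFS from EOT in the four ctDNA-by-PET cells, so that the comparison rests on the discordant cells.
3. Add sensitivity analyses that exclude, or show separately, patients given residual PET radiotherapy, and that count non-protocol anti-lymphoma therapy as failure and then censor at it. Never-irradiated patients should not become the primary set. That would select on a discretionary decision made after the test, and would leave in patients with three or more sites, new sites or little shrinkage.
4. Limit any interim-PET claim to patients for whom the Day 53 scan is required (paediatric patients and those with declared radiotherapy intent; Sections 7.4b and 9.1).

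The cost is SAP wording and a few extra tables, with no new data and no change to patient management. The downside is wide intervals in small cells: with about 19 non-irradiated PET-positive patients (40 - 20.9), the worst-case half-width is 1.96 x sqrt(0.25/19), about 22 points.

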The S1826 study will accrue 470 eligible patients per arm. Based on previous data, the 2-year PFS after BV-AVD is estimated to be approximately 82%. An exponential cure rate model is assumed for both arms. In addition, among the fraction of patients with disease progression, a hazard ratio of 1.67 is assumed between the arms. Under the above assumptions, for the proposed initial sampling size of 400 patients (accrued during the first half of study accrual) with samples and designed follow-up, we assume that there will be a total of 94 PFS events across both arms under the alternative hypothesis. Hence, we believe most power calculations are conservative.

Objective 1: To test if the treatment effect of N-AVD versus BV-AVD on PFS depends on specific genetic alterations, we will power this analysis using 9p24.1 amplification, which are characteristic in cHL. We assume 400 patients with evaluable samples and similar follow-up by study design. Based on our prior work, 9p24.1 amplification will be present in 50% of advanced stage cHL patients.(18) Based on its established prognostic impact in standard frontline chemotherapy-based treatment of cHL, it is assumed that 9p24.1 alteration will be positively associated with PFS after N-AVD but not after BV-AVD. A two-sample, two-sided level .05 of a Cox Regression score test of the interaction for patients with and without 9p24.1 amplification has power of approximately 80% to detect an interaction ratio of hazard ratios of 3.3. In addition, we will test the prognostic association in each of the treatment groups. Testing the prognostic association within the BV-AVD group, a two-sample log-rank test for patients as defined by 9p24.1 amplification among BV-AVD patients has power of approximately 90% to detect a hazard ratio of 2.5. In both analyses, the magnitude effect sizes are critical for interpretation and 95% confidence intervals will be presented. In addition, we will use descriptive statistics to characterize the frequency of each type of genetic alteration at baseline in the S1826 cohort, and evaluate associations with outcome.

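### At a PPV of 0.5, the ±11% precision for end-of-treatment PPV fits ctDNA with both arms pooled; it does not carry over to PET-CT or to a single arm

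*Combined protocol and SAP*

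**What the plan says.** The text is in the combined protocol and SAP, Section 18.13d, at the end of Objective 2. It compares the PPV and NPV of detectable ctDNA at the end of treatment with those of the end-of-treatment PET-CT response. It assumes "approximately 20% of patients will be ctDNA positive at EOT, and 10% will be PET-CT positive".

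The precision statement begins "With approximately 200 patient samples per arm, then the PPV for either of those measures can be estimated to within +/- 11" percent. Read to its end, it says that "the PPV for either of those measures can be estimated to within +/- 11% (95% confidence interval) for the case with 20% ctDNA positive". The next sentence is "Analogous results hold for PET-CT and NPV". No half-width is given for PET-CT or for NPV. No PPV is assumed, and nothing says whether PPV is to be estimated within each arm or with the arms combined.

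The total comes from Objective 1 in the same section: "We assume 400 patients with evaluable samples and similar follow-up by study design". The hypothesis that the comparison serves is in Section 18.13b, which expects molecular tumor burden at the end of treatment to outperform PET-CT on both PPV and NPV.

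**The concern.** The precision of a PPV depends on how many patients test positive, not on how many are sampled. The sentence cites a per-arm sample size, names both tests and gives one half-width, although the plan expects half as many PET-CT positives as ctDNA positives. One half-width cannot serve both tests at the same PPV, and the cited per-arm size does not produce it at the usual planning value.

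At stake is what a reader expects from the comparison. PET-CT is the less precise side, and it is the side with no figure. Arm-specific precision may also matter. Section 7.4c says the predictive value of a positive end-of-treatment PET-CT under nivolumab is not known, and it warns that false positives may be frequent in Arm 1. If the PET-CT PPV differs by arm, a pooled estimate averages two different quantities, and the per-arm precision becomes the relevant one.

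**Working it through.** **Inputs from Section 18.13d.** ctDNA-positive rate 20%; PET-CT-positive rate 10%; about 200 samples per arm; 400 patients in total; two-sided 95% interval.

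**Assumption.** The plan gives no PPV. I use 0.5, which is the worst case and the usual planning convention, and then show a range.

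**Formula.** Half-width = 1.96 × √[p(1 − p)/n], where n is the number of test-positive patients for PPV and of test-negative patients for NPV.

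**Reproducing the plan's figure.** ctDNA, arms pooled: n = 0.20 × 400 = 80, and 1.96 × √(0.25/80) = 11.0%. This matches. In reverse, a half-width of 11% at p = 0.5 needs n = 0.25 × (1.96/0.11)² ≈ 79.4.

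**Same formula with the other counts.**
- ctDNA, one arm: n = 0.20 × 200 = 40, giving 15.5%.
- PET-CT, pooled: n = 0.10 × 400 = 40, giving 15.5%.
- PET-CT, one arm: n = 0.10 × 200 = 20, giving 21.9%.

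At any common PPV and on the same pooling, the PET-CT half-width is √2 ≈ 1.41 times that of ctDNA, because it has half the positives.

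**Other interval methods at p = 0.5.** With 40 positives, Wilson gives 14.8%, Clopper-Pearson 16.2%, and a 90% interval 13.0%. None gives 11%. With 80 positives, Wilson gives 10.7% and Clopper-Pearson 11.4%.

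**NPV at 0.5.** ctDNA: n = 320 pooled, 5.5%; n = 160 per arm, 7.7%. PET-CT: n = 360 pooled, 5.2%; n = 180 per arm, 7.3%.

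**Sensitivity to the unstated PPV (half-width, %).**

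| Positives | PPV 0.5 | 0.7 | 0.85 | 0.9 |
|---|---|---|---|---|
| 80 (ctDNA pooled) | 11.0 | 10.0 | 7.8 | 6.6 |
| 40 (ctDNA per arm; PET-CT pooled) | 15.5 | 14.2 | 11.1 | 9.3 |
| 20 (PET-CT per arm) | 21.9 | 20.1 | 15.6 | 13.1 |

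With 40 positives, 11% is reached only if the PPV is about 0.85 or higher (or 0.15 or lower). With 20 positives it takes about 0.93 or higher (or 0.07 or lower).

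**The case against.** Four points count against a harsher reading.

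- **The qualifier.** A reader might infer that the plan claims ±11% for PET-CT at 10% positive. It does not plainly do so. The sentence ends by limiting the figure to the 20% ctDNA scenario, and the follow-on sentence can mean the same calculation with different counts. This stands. What remains is that naming both tests sits badly with the qualifier, and the reader is given no PET-CT figure.
- **Pooling.** A reader might infer that the 11% is an arithmetic error. The per-arm size may only describe how the 400-patient set divides, and Objective 2 is framed across both regimens. On that reading 11% is correct for ctDNA. This also stands, but the text never says that PPV is pooled. The nearby wording about combining the arms with stratification belongs to the log-rank test at Cycle 3 Day 1.
- **The assumed PPV.** A reader might infer that 11% is unattainable except for pooled ctDNA. That depends on a PPV near 0.5. At a PPV of 0.9, both per-arm ctDNA and pooled PET-CT reach 9.3%. However, the plan states no such value, Section 7.4c gives no support for a high PET-CT PPV in Arm 1, and 0.5 is the value that reproduces the plan's own figure.
- **The comparison itself.** Both tests are read in the same patients, so separate half-widths do not give the precision of the paired difference. This is correct, and the figures here should not be used for that purpose. Nor does any sample size or decision rule rest on the 11%.

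**Conclusion.** The point holds as a minor correction. Taking a PPV of 0.5, the plan's ±11% is the precision for ctDNA with both arms pooled. The cited per-arm size gives ±15.5%. For PET-CT, at the plan's own positive rate, ±11% is not reached either pooled or per arm at that PPV: the half-widths are 1.4 and 2.0 times the stated value. The defects are an unstated basis for the ctDNA figure and a loose extension to PET-CT and NPV, for which pooled and per-arm half-widths at 0.5 run from about 5% to 22%.

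The conclusion rests on the plan's assumed positive rates, 400 evaluable patients split evenly between the arms, and the worst-case PPV. It concerns a secondary correlative comparison only. The primary PFS analysis and the primary molecular tumor burden analysis (the 2-log change at Cycle 3 Day 1) are unaffected.

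**What to change.** In Section 18.13d, Objective 2:

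- State that ±11% is the 95% half-width for the ctDNA PPV with arms pooled (80 positives), at an assumed PPV of 0.5.
- Add ctDNA PPV per arm, ±15.5% (40 positives).
- Add PET-CT PPV, ±15.5% pooled (40 positives) and ±22% per arm (20 positives).
- Add pooled NPV at 0.5, ±5.5% for ctDNA and ±5.2% for PET-CT.
- Say whether PPV and NPV will be reported pooled, by arm, or both.
- Delete the words that apply the single figure to both tests, and delete the sentence "Analogous results hold for PET-CT and NPV".

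If the authors expect a PPV well away from 0.5, they should state it and recompute the half-widths on that basis.

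The cost is a text edit. No design, sample or analysis changes. The stated precision for PET-CT and for single-arm estimates becomes less favourable; the pooled ctDNA figure stays as it is.
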